## 8. Sample Size Calculations

The study population includes men with erectile dysfunction attributable to an underlying, stable medical condition but who are otherwise in good health. The most common stable medical diseases that cause erectile dysfunction include hypertension and atherosclerosis, antihypertensive medication, type I and type II diabetes mellitus, pelvic surgery and pelvic radiation, cerebrovascular accidents (stroke), multiple sclerosis, and Parkinson's disease. Men with erectile dysfunction secondary to aging as a solitary cause will not be included in the trial. Serum Prolactin levels will have been obtained on the participants as part of their work up for erectile dysfunction. The target population is men with erectile dysfunction who have been unable to tolerate, do not wish to continue, or have had unsuccessful results with, prior therapy for ED.

The sample size has been estimated assuming a standard deviation of 2.5 and a two sample t-test to have 80% power.

Statistical Power									
Power	N1	N2	Placebo	Ratio	Alpha'	Mean1	Mean2	SD1	SD2
80%	11	11	13	1.111	0.0167	10.0	6.6	2.5	2.5

Alpha' is the alpha level adjusted for three multiple comparisons (the two doses compared with each other, each dose compared with the placebo, and total active treatment (two doses combined) compared to placebo. Given the three comparisons that incorporated a Bonferroni multiple comparison procedure, the overall alpha level is preserved at .05.

A 10% attrition rate over the 24 weeks of follow-up is anticipated, which inflates the sample size to approximately 40 subjects in total.

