### ION04ED

If a patient has repeated assessments prior to the start of double-blind study drug, then the results from the final assessment made prior to the start of double-blind study drug will be used as baseline. If end-of-study assessments are repeated or unscheduled, the last post-baseline assessment will be used as the end-of-study assessment for generating summary statistics. However, all post-baseline assessments will be presented in the data listings.

Dose response comparisons will be made between 8000 mcg vs. 16000 mcg vs. placebo as well as comparisons between total active population (8000 mcg and 16000) vs. placebo. Onset and duration of effect will also be analyzed and a dose response evaluated. Onset and duration of action will also be analyzed.

All tests of significance with regard to efficacy will be one-tailed, and performed at an overall alpha level of .05. All estimates of differences will be presented with 95% confidence limits.

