#### **Erectile Function (EF) domain of the International Index of Erectile Function (IIEF)**

The erectile function domain, questions 1-5, and 15 of the IIEF has been validated to assess erectile changes only. The IIEF EF domain has a 30-point total score, where higher scores reflect better erectile function. The EF domain of the IIEF will be completed at Visit 1 (screening) and V2-V7 (week 0-24).

The total score for a subject for the EF domain will be computed as the sum of the six questions. Descriptive statistics of the domain score will be presented with respect to the subjects receiving *hMaxi-K* (16,000 µg) and placebo at all visits. The change in scores from baseline at each visit will be evaluated using one-sided paired t-test at 5% significance level to assess improvement in scores post treatment when compared to baseline for the two treatment groups separately. Further, a one-sided two sample t-test will be applied to compare the changes from baseline in scores between the two treatment groups. The scores for the other 4 domains on the IIEF will also be computed and analyzed as secondary analyses.

Repeated measures ANOVA will be performed to assess the effect of visit on the total score for each treatment groups. Further a two-sample t test, will be performed to study the effect of treatment groups and time points on the domain scores.

The above analysis will be repeated for comparison between the two treatment cohorts and between *hMaxi-K* 8000µg and placebo treatment groups.

Analysis will be performed including all subjects and the final 15 subjects separately.

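### Fix the family of treatment contrasts as the three placebo comparisons in SAP 9.3 and test it by Holm's step-down; flat Bonferroni at 0.0167 gives up power and sits on an inconsistent list

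*SAP*

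**What the plan says.** SAP section 8 sizes the trial by a two-sample t-test with 80% power and SD 2.5, at alpha' = 0.0167, with 11, 11 and 13 men. It describes the level so: "Alpha' is the alpha level adjusted for three multiple comparisons". The bracket that follows names "the two doses compared with each other, each dose compared with the placebo, and total active treatment (two doses combined) compared to placebo". That is four contrasts. The section then concludes: "Given the three comparisons that incorporated a Bonferroni multiple comparison procedure, the overall alpha level is preserved at .05".

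Protocol 10.3.2 has the same table and level, but its bracket holds only three contrasts: dose against dose, and each dose against placebo.

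The opening of SAP section 9 says: "All tests of significance with regard to efficacy will be one-tailed, and performed at an overall alpha level of .05". It plans dose-response comparisons across 8,000 µg, 16,000 µg and placebo, plus pooled active against placebo, and promises 95% confidence limits for all differences. It names no multiplicity procedure.

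SAP 9.3, for the EF domain, compares changes from baseline between 16,000 µg and placebo by a one-sided two-sample t-test. It then adds: "The above analysis will be repeated for comparison between the two treatment cohorts and between" 8,000 µg and placebo. The SEP part has the same structure. Neither part has a test of 8,000 against 16,000 µg. The only level written in 9.3 is 5%, attached to the within-group paired test.

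**The concern.** The analyst who runs the between-group tests must know which contrasts share the overall .05 and how. The documents give two lists of four and two lists of three, and the two lists of three differ. The Bonferroni level appears only in the sample-size text.

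Even with the family settled, flat Bonferroni is not the best use of the error allowance. For any fixed family, Holm's step-down controls the same overall error and rejects at least as much. With 35 men in three arms, power that can be had by wording alone is worth taking, above all for the 8,000 µg dose and for a claim about both doses.

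**Working it through.** **Inputs.** From the SAP section 8 table (identical in Protocol Table 2): means 10.0 and 6.6, so a difference of 3.4; SD 2.5 in both groups; arms 11/11/13; alpha' 0.0167. From SAP section 9: one-tailed tests, overall .05. The documents give no separate effect for 8,000 µg, so I take 3.4, 1.7 and 0 as a range, with 16,000 µg fixed at 3.4.

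**Step 1: the plan's own figure.** 0.05/3 = 0.0167. For 11 against 13, the standard error is 2.5 × √(1/11 + 1/13) = 1.024 and the noncentrality 3.4/1.024 = 3.32 on 22 degrees of freedom. One-sided power at 0.0167 is 84.6%. At the stated ratio of 1.111, the smallest active arm that reaches 80% is 11, with placebo 11 × 1.111 = 12.2, rounded up to 13. The stated sizes reproduce.

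**Step 2: the family, side by side.**

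| Contrast | SAP 8 | Protocol 10.3.2 | SAP 9 opening | SAP 9.3 |
|---|---|---|---|---|
| 16,000 µg v placebo | yes | yes | yes | tested |
| 8,000 µg v placebo | yes | yes | yes | tested |
| Pooled active v placebo | yes | no | yes | tested |
| 8,000 v 16,000 µg | yes | yes | yes, no test named | no |
| Count | 4 | 3 | 4 | 3 |

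Bonferroni on four contrasts would be 0.05/4 = 0.0125. The stated 0.0167 used four times sums to 4 × 0.0167 = 0.067, above the .05 that the Bonferroni argument needs. On the three contrasts that 9.3 tests, it is again 0.05/3 = 0.0167.

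**Step 3: Holm on the three placebo contrasts.** Order the three p-values. Compare the smallest with 0.05/3 = 0.0167, the next with 0.05/2 = 0.025 and the largest with 0.05, stopping at the first failure. The first threshold equals the flat level and the later ones are larger, so every flat-rule rejection is also a Holm rejection. The first step is the same, so the chance of at least one rejection is the same too.

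**Step 4: size.** Simulation with one-sided pooled-variance t-tests, 11/11/13, SD 2.5 (200,000 trials; the last column and the rates below the table come mainly from a 100,000-trial run). Power in per cent:

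| Assumed 8,000 µg effect | Result sought | Flat 0.0167 | Holm, three placebo contrasts | Holm, all four of SAP 8 |
|---|---|---|---|---|
| 3.4 | 16,000 µg v placebo | 84.5 | 92.3 | 87.3 |
| 3.4 | both doses v placebo | 74.8 | 89.0 | 81.2 |
| 1.7 | 16,000 µg v placebo | 84.4 | 86.5 | 83.0 |
| 1.7 | 8,000 µg v placebo | 29.0 | 47.5 | 37.9 |
| 0 | 16,000 µg v placebo | 84.6 | 84.7 | 83.3 |

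The flat figures for 16,000 µg differ between rows only by simulation error around the exact 84.6%. On the three placebo contrasts, the chance of at least one rejection is 96.1%, 87.3% and 84.6% for effects of 3.4, 1.7 and 0, under either rule. With no effect anywhere, the overall error is about 3.5% under either rule.

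Holm on all four contrasts starts at 0.0125. For 16,000 µg it falls below the flat 0.0167 rule in the half-effect and no-effect rows.

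The sample-size table does not state sidedness. With two-sided tests and both doses effective, the gains are of similar size: 76.1% to 85.7% for 16,000 µg, and 62.9% to 80.0% for both doses.

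**The case against.** The best defence is that Bonferroni is simple, valid and conservative, and that a small phase 2A trial may choose it. SAP section 4 makes 16,000 µg against placebo the primary comparison, and showing both doses superior is not a stated objective. On the primary comparison the gain is large only if 8,000 µg works about as well: roughly two points at half effect, and nothing of note if 8,000 µg is inert. Bonferroni also has simple simultaneous intervals that match its tests, and Holm does not. All of this stands, and it is why the point is an efficiency gain.

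The interval argument is weaker here than usual. The SAP promises plain 95% limits with no adjustment described, so its intervals do not match tests at 0.0167 as it is.

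Three stronger readings are tempting.

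- A reader might infer that dose against dose uses up a third of the alpha and that dropping it frees that share. This fits the protocol's list only. Once pooled active against placebo is counted, as SAP 8, 9 and 9.3 all do, three contrasts remain and the first-step level is still 0.0167. The gain comes from stepping down.
- A reader might infer that the dose comparison has been abandoned. The opening of SAP section 9 still plans it; only a test in 9.3 is missing.
- A reader might infer that every placebo contrast will be tested at 0.0167. SAP 9 and 9.3 do not say so. The comparison above takes the sample-size text as the intended rule.

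**Conclusion.** The point holds as a cheap improvement. SAP 8, SAP 9.3 and Protocol 10.3.2 do not agree on the family of treatment contrasts, and no level is attached to the between-group tests. With the family set to the three placebo contrasts of 9.3, Holm is never worse than flat 0.0167. It adds between nothing and about 8 points for 16,000 µg, about 14 points for showing both doses when both are fully effective (74.8% to 89.0%), and about 18 points for 8,000 µg at half effect (29.0% to 47.5%). These figures rest on the plan's 3.4 and 2.5, on 11/11/13 men analysed, and on the assumed 8,000 µg effects.

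A reader might go further and say that the overall error exceeds .05 because four contrasts are listed and three are counted. The Bonferroni sum does not guarantee .05 for four, but the contrasts are correlated, and simulated error with no effect in any arm is 4.8% for all four at 0.0167. The documents do not support calling the Bonferroni rule an error. Nor is Holm free of cost, or better on any list: applied to SAP 8's four contrasts it can lower power for 16,000 µg (84.4% to 83.0% at half effect).

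The point does not touch multiplicity over visits, or over EF, SEP2 and SEP3.

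**What to change.** Before the treatment code is broken, make SAP 8, 9 and 9.3 and Protocol 10.3.2 say the same thing:

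1. The tested family is 16,000 µg, 8,000 µg and pooled active, each against placebo, on EF change at whichever time point is designated primary. SAP 9.3 tests every visit and designates none, so that choice has to be written down as well.
2. The family is tested by Holm's step-down at overall one-sided .05 (0.0167, 0.025, 0.05), in place of flat Bonferroni. State this in SAP 9.3, where the tests are.
3. 8,000 against 16,000 µg is reported as an estimate with confidence limits. This serves the dose-response comparison in SAP 9.
4. Holm is not applied to the four contrasts now listed in SAP 8.

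The sample-size table can stay, because 0.0167 is still the first-step level and the stated power becomes a floor for each placebo contrast.

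The cost is SAP and protocol wording, with no added men, visits or data. Two downsides should be accepted openly: dose against dose has no formal test, and Holm can occasionally reject where a Bonferroni-level interval still includes zero.

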## 9. Statistical Methods

This section describes the various statistical analyses that are planned to be performed for this study. The primary analysis which includes efficacy analysis will be performed on the mod-ITT population and supportive analysis on the PP and ITT populations. The safety endpoints will be evaluated on the safety population.

### ION04ED

If a patient has repeated assessments prior to the start of double-blind study drug, then the results from the final assessment made prior to the start of double-blind study drug will be used as baseline. If end-of-study assessments are repeated or unscheduled, the last post-baseline assessment will be used as the end-of-study assessment for generating summary statistics. However, all post-baseline assessments will be presented in the data listings.

Dose response comparisons will be made between 8000 mcg vs. 16000 mcg vs. placebo as well as comparisons between total active population (8000 mcg and 16000) vs. placebo. Onset and duration of effect will also be analyzed and a dose response evaluated. Onset and duration of action will also be analyzed.

All tests of significance with regard to efficacy will be one-tailed, and performed at an overall alpha level of .05. All estimates of differences will be presented with 95% confidence limits.

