### 9.3. Primary Analysis

The primary outcome measures that will be considered to evaluate change in erectile status from baseline following administration of *hMaxi-K* are

- Erectile Function (EF) domain of the International Index of Erectile Function (IIEF)
- Sexual Encounter Profile (SEP): Questions 2 and 3

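### The SAP claims an overall one-sided .05 for efficacy, but its 0.0167 covers treatment contrasts only: visits and the three unordered primary outcomes are left uncontrolled

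*SAP*

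**What the plan says.** **The claim.** SAP section 9 says: "All tests of significance with regard to efficacy will be one-tailed, and performed at an overall alpha level of .05". SAP section 8 says: "Given the three comparisons that incorporated a Bonferroni multiple comparison procedure, the overall alpha level is preserved at .05".

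**What is adjusted for.** SAP section 8 describes Alpha' = 0.0167 as "adjusted for three multiple comparisons (the two doses compared with each other, each dose compared with the placebo, and total active treatment" versus placebo. That is four comparisons: dose versus dose, each of two doses versus placebo, and pooled active versus placebo. Protocol 10.3.2 gives the same 0.0167 for three: dose versus dose, and each dose versus placebo. Neither list mentions visits or outcomes.

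**What is tested.**
- SAP 9.3 introduces "The primary outcome measures that will be considered to evaluate change in erectile status from baseline" and lists the EF domain and SEP questions 2 and 3, with no order.
- For EF it says: "The change in scores from baseline at each visit will be evaluated using one-sided paired t-test at 5% significance level". Then: "Further, a one-sided two sample t-test will be applied to compare the changes from baseline in scores between the two treatment groups". This is written for 16,000 µg and placebo, and is repeated for pooled active versus placebo and for 8,000 µg versus placebo.
- The post-dose visits are V3 to V7 (weeks 1, 4, 8, 12 and 24). No visit is named as primary.
- SAP section 9 adds: "Dose response comparisons will be made between 8000 mcg vs. 16000 mcg vs. placebo as well as comparisons between total active population" versus placebo.
- The EF analysis is also run separately in the final 15 subjects.

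**What is primary.** Protocol 2.0 makes safety primary and efficacy secondary. The protocol synopsis lists EF, SEP2 and SEP3 as primary outcomes. SAP section 4 makes efficacy and safety of 16,000 µg versus placebo the primary objective.

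**The concern.** An overall error rate has meaning only for a defined set of tests. The SAP promises .05 for all efficacy tests, yet the one adjustment it makes divides alpha among treatment comparisons. For EF alone, SAP 9.3 describes 3 placebo contrasts × 5 visits = 15 between-group tests, and SEP2 and SEP3 come on top. Nothing says which of these decides whether the trial is positive.

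With 11 to 13 participants per arm, one isolated significant visit is a realistic chance result. Under the present text a reader could not attach the stated .05 to it. The mismatch between four listed comparisons and a divisor of three adds a second doubt: what the 0.0167 is meant to cover.

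**Working it through.** **1. The plan's own figures.**
- 0.05 / 3 = 0.0167, as stated. For four comparisons it would be 0.05 / 4 = 0.0125.
- Power, noncentral t, one-sided 0.0167, difference 10.0 − 6.6 = 3.4, SD 2.5 (standardised 3.4 / 2.5 = 1.36): 81.0% for 11 v 11 and 84.6% for 11 v 13. The stated 80% is reproduced.
- Attrition: 35 / 0.9 ≈ 39, consistent with about 40.

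**2. Set-up for the error rate.**
- From the documents: arms 11 (16,000 µg), 11 (8,000 µg) and 13 (placebo); five post-dose visits; one-sided two-sample t-tests; 0.0167 per test.
- Assumed: normally distributed changes and equal correlation ρ between visits, from 0.5 to 0.9. The documents give no value.
- Quantity: the probability, with no effect in any arm, that at least one test in the set has T > t(1 − 0.0167, df). Here df = 22 for one dose versus placebo, 33 for pooled active versus placebo and 20 for dose versus dose.
- Method: simulation, 60,000 to 200,000 null trials per setting.

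**3. One visit, one outcome** (does not depend on ρ).

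| Set of tests at 0.0167 | Error |
|---|---|
| Three placebo contrasts | about 3.4-3.5% |
| Three pairwise comparisons (protocol list) | about 4.5% |
| All four comparisons (SAP list) | about 4.8% |

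The Bonferroni bound for four tests is 4 × 0.0167 = 6.7%, so the stated procedure does not guarantee .05 for four. The realised error is nevertheless just under .05, because the contrasts share data.

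**4. EF over five visits at 0.0167 per test.**

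| ρ | 16,000 µg v placebo (5 tests) | Three placebo contrasts (15 tests) |
|---|---|---|
| 0.5 | about 6.5% | about 12.6% |
| 0.7 | about 5.3% | about 10.3% |
| 0.8 | about 4.6% | about 9.0% |
| 0.9 | about 3.6% | about 7.1% |

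Across separate runs the first column spans 3.5-6.7% and the second about 7-13%. The first falls below 5% near ρ = 0.75. The second is still about 6% at ρ = 0.95 and reaches 5% only slightly above 0.97. With correlation that decays between visits (AR(1), 0.5 to 0.9) the second column is about 14% to 8%.

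**5. Outcomes.** Take EF, SEP2 and SEP3 with one test each at 0.0167, treated as normal with an assumed correlation of 0.5 to 0.9. The error is 8.8% to 5.9% over the three placebo contrasts and 4.5% to 2.9% for 16,000 µg versus placebo alone.

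**The case against.** The strongest reply is that SAP section 4 makes 16,000 µg versus placebo the primary objective and SAP 9.3 describes that contrast first. For it alone the error over five visits is 3.5-6.7%, so .05 is roughly met over much of the assumed range. SAP section 9 also plans to describe onset and duration of effect, which is a legitimate reason to show every visit. The study is Phase 2A, and no go/no-go rule uses these p-values. All of this stands, and it limits the severity. It does not remove the point: an objective is not a testing order, and SAP 9.3 sets none.

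A reader might draw four stronger conclusions that the documents do not support.
- *The error rate is 7-13%.* That needs any of the 15 EF tests to count as a positive result. The documents do not say that it would, nor that it would not.
- *Between-group tests run at 5% each, giving 17-29% over 15 tests.* The 5% in SAP 9.3 belongs to the within-group paired tests. SAP section 8 ties 0.0167 to a two-sample t-test, which is the between-group test, so these figures carry little weight.
- *The dose-versus-dose test was dropped.* It is absent from SAP 9.3, but the opening text of SAP section 9 plans it. The defect is the count and the mismatch between sections.
- *Leaving out the protocol's mixed or marginal model for EF created the problem.* Protocol 10.3.2 uses that model for trends and also compares changes at all visits, so visit-by-visit testing was already there.

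The reason for the final-15 analysis may lie in SAP section 10 or the table shells, which were not available. Its absence from the text is not held against the plan.

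**Conclusion.** The .05 statement is wrong as written and should be fixed. It is true on a narrow reading: one outcome, one visit, each contrast at 0.0167 (about 3.5% to 5%). For 16,000 µg versus placebo over five visits it is borderline. It fails, at about 7-13%, if any placebo contrast at any visit may count. The SAP does not say which reading applies.

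The five-visit figures rest on the assumed correlation of 0.5-0.9, normal outcomes and 0.0167 per test. The mismatch between four listed and three counted comparisons, and the lack of a primary visit and outcome order, can be read directly from the text and need no assumption.

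**What to change.** Protocol 10.3 says the final SAP is issued before the treatment code is broken. Make these changes by then.

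1. In SAP 9.3, name one primary EF analysis in the Mod-ITT population. It can be change from baseline at one named visit, or one across-visit treatment estimate from the protocol's mixed or marginal model. If a visit is chosen, it should be the one behind 10.0 versus 6.6; the documents attach none, so the sponsor must state it.
2. Make 16,000 µg versus placebo the primary test, in line with SAP section 4, and test the other comparisons in a fixed order. Alternatively, keep 0.0167 for exactly three listed comparisons, or use 0.0125 if all four stay.
3. Label other visits, SEP2, SEP3, within-group tests and the final-15 analysis as secondary or descriptive, with no claim of error control. If the sponsor does not want this, withdraw the overall .05 statement.
4. Make the list in SAP section 8 agree with its count and with the contrasts in sections 9 and 9.3.
5. Reconcile the primary objective across Protocol 2.0, the synopsis and SAP section 4.
6. SAP section 9 says: "All estimates of differences will be presented with 95% confidence limits". If 0.0167 is kept, note that the matching two-sided limits are 1 − 2 × 0.0167 = 96.7%.

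**Cost.** Wording in the SAP and a clarification of objectives in the protocol; no new data or participants. One-sided power at difference 3.4 and SD 2.5, before and after about 10% attrition:

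| Comparison and level | Planned n | After attrition |
|---|---|---|
| Dose v placebo, 0.0167 | 85% (11 v 13) | 81% (10 v 12) |
| Dose v dose, 0.0167 | 81% (11 v 11) | 76% (10 v 10) |
| Dose v placebo, 0.0125 | 81% (11 v 13) | 77% (10 v 12) |
| 16,000 µg v placebo as first test in a fixed order, 0.05 | 94% (11 v 13) | 92% (10 v 12) |

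At 0.0167 the planned 80% therefore survives attrition only for the placebo comparisons. Splitting 0.0167 over five visits (0.0167 / 5 = 0.0033) would give 63% and 57% for dose versus placebo, so naming one analysis is much cheaper. The downside is that other visits, outcomes and contrasts outside the named set lose confirmatory status.
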